### I. Background:

Knee osteoarthritis (OA) is an extremely common cause of disability, with a global prevalence of 22.9% in adults aged 40 and over. OA is a whole-joint disease characterized by progressive degradation of articular cartilage, chronic inflammation of joint tissue, and subchondral bone remodeling, resulting in severe pain and decreased mobility in patients.

No cure currently exists for OA, and treatment is aimed at symptomatic management and prevention of disease progression. Currently, this consists of:

1. Initial conservative treatment for osteoarthritis across all levels of radiographic disease severity includes activity modification, oral analgesic or anti-inflammatory medications, non-supervised or supervised (e.g., physical therapy) exercise, and occasionally bracing.
2. Injection therapies have been used in the treatment of osteoarthritis for more than 60 years. Medical corticosteroids have served as a gold standard for symptom management as an intra-articular injection, but concerns have always existed around the potential for either the steroid medication (which suppresses both repair and inflammation processes) or the local anesthetic co-administered with the steroid to contribute to degradation of joint cartilage over time. Alternative substances have been developed to address the joint environment – with an intent to improve symptoms, while decreasing the potential for joint degeneration. These alternative medications include viscosupplements (hyaluronic acid analogues) and biological agents (platelet-rich plasma, or stem cell therapies).
3. Surgical interventions include arthroscopy for concurrent symptomatic meniscus tears or unstable cartilage that contribute to mechanical symptoms, osteotomy (realignment) surgery for active patients with single compartment arthritis, and arthroplasty (joint replacement) for

patients with more limited activity goals, severe arthritis, and temporary—but not sustained--pain relief with the conservative treatments described in #1 and #2.

Intra-articular injection of a corticosteroid has been shown to be effective in providing short-term relief of knee OA symptoms, possibly due to anti-inflammatory and immunosuppressive effects. Repeated corticosteroid injections have thus become the standard of care for patients with mild to moderate knee OA.

Intra-articular injection of platelet-rich plasma (PRP) has emerged as a promising alternative to corticosteroid injection in knee OA patients. Studies have indicated that PRP is safe and may provide benefits such as pain relief, improved knee function, and enhanced quality of life. Moreover, PRP injection has been shown to provide longer-lasting symptomatic attenuation, with clinically significant improvement observed for as long as 12 months post-injection.

Previous studies have indicated that concentrations of inflammatory and degradative biomarkers in patient serum, urine, and synovial fluid may provide insight into OA pathophysiology. To our knowledge, no study has been performed to assess the impact of intra-articular PRP injection upon fluid concentrations of a comprehensive panel of proposed OA-related biomarkers. In this study, we will evaluate the impact of intra-articular PRP injection upon markers of cartilage matrix turnover, inflammatory mediators, degradative enzymes, inhibitors of degradative enzymes, and markers of bone metabolism in serum, urine, and synovial fluid of knee OA patients.

### **Objectives:**

#### Primary objective:

- To evaluate the effect of intra-articular PRP injection upon serum, urine, and synovial fluid MCP-1 concentrations in knee OA patients
  - Previous studies have indicated that this inflammatory biomarker may be significantly decreased from baseline in the serum of knee OA patients after receiving intra-articular PRP injections, when measured three months after a patient's final injection. Monitoring fluid biomarker concentration provides insight into the joint environment and may correspond to clinical outcomes.

#### Secondary objectives:

- To examine the effect of PRP injection upon serum, urine, and synovial fluid concentrations of additional pro-inflammatory biomarkers in knee OA patients
  - Other pro-inflammatory markers of interest in fluids of knee osteoarthritis patients include RANTES, IL-1b, IL-6, IL-8, TNF-a, MIP-1a, and PGE2. Each of these proteins plays a unique role in the inflammatory cascade and can provide insight into the inflammatory status of the joint.

- To evaluate the effect of PRP injection upon serum, urine, and synovial fluid concentrations of anti-inflammatory biomarkers in knee OA patients
  - In contrast, IL-1RA, IL-4, and IL-10 act through pathways to reduce inflammation. Measuring levels of these proteins affords increased insight into inflammatory status.
- To assess the effect of PRP injection upon serum, urine, and synovial fluid concentrations of other pro-degradative biomarkers in knee OA patients
  - Cartilage degradation by matrix metalloproteinases (MMPs) is a significant component of OA progression, and analysis of these enzymes is critical in understanding this component of OA pathophysiology.
- To evaluate the effect of PRP injection upon serum, urine, and synovial fluid concentrations of anti-degradative biomarkers in knee OA patients
  - TIMP-1 and TIMP-2 are proteins that inhibit degradation within the joint and are therefore relevant to the monitoring of OA progression.
- To examine the effect of PRP injection upon serum, urine, and synovial fluid concentrations of cartilage matrix proteins in knee OA patients
  - Collagen and proteoglycan are key components of the extracellular matrix of cartilage. Assessing COMP, CTX-I, CTX-II, PIICP, and HA concentrations provides further insight into the balance between anabolism and catabolism of these components.
- To assess differences in patient serum, urine, and synovial fluid biomarker concentrations between single- and double-PRP injections
- To evaluate the impact of PRP injection upon patient-reported outcome measures
- To evaluate relationships between baseline patient biomarker concentrations and treatment efficacy, based on patient-reported outcome measures, following PRP or corticosteroid injection

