## II. Drugs/Biologics/Devices

The biologic under investigation in this study is platelet-rich plasma (PRP), a concentrated solution of platelets of autologous origin. This product will be produced from approximately 15 milliliters of whole blood by a venous blood draw performed by a clinical medical staff within the patient exam room. This sample will be placed into a centrifuge located in the clinical office to collate the platelets within the sample for proper collection of PRP. The 15 milliliters of whole blood will produce approximately 4-6 milliliters of PRP. The volume of PRP administered will be approximately 4-6 milliliters via intraarticular injection in the affected knee of patients with moderate-to-severe knee OA. This amount of PRP is indicated because standard knee injections (a large joint injection) range from 5-10 milliliters of medical substance. The PRP will be administered during the initial visit.

The current standard of care for treatment of moderate-to-severe knee OA involves serial, intra-articular injection of a corticosteroid, with injections performed, at minimum, three months apart. This modality has been shown to provide short-term relief of knee OA symptoms, possibly by modulating the immune response and associated inflammatory cascade and will be used as the reference therapy in this study. However, a limitation of this treatment is a lack of understanding of its impact upon OA pathophysiology, and specifically cartilage degeneration. PRP has been

selected for this study because it has been shown to provide pain relief and increase functionality when administered as described. Moreover, its beneficial effect may persist longer than that of corticosteroid injection, as well as remove the potential for cartilage degradation associated with intraarticular corticosteroid treatment. A corticosteroid study arm is also implemented to compare standard of care treatment to the PRP treatment population.

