## **VI. Number of Subjects:**

Approximately 70 participants will be enrolled. 35 to each arm if funding allows.

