## **VII. Study Procedures/Methods:**

### Enrollment/Randomization/Treatment Visit:

Eligible patients with primary osteoarthritis in at least one knee will be enrolled on a voluntary basis. Prior to the injection, patient-reported outcomes will be quantified using a visual-analog scale (VAS) to assess pain level, a Knee Injury and Osteoarthritis Outcome Score-Joint Replacement (KOOS-JR), and UCLA Activity score to assess functional activity level as part of standard care. These results will be deidentified and analyzed in the laboratory.

The patient will be randomized into one of two treatment arms. If the patient has a history of receiving bilateral knee injections for osteoarthritis and meets study requirements, randomization will occur for both knees. Randomization will be employed using a computer-generated random assignment sequence and results kept in concealed envelopes. The participant will be blinded to the injection regime received.

Enrolled patients will be randomized to one of two treatment arms:

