**Deleted: ¶**

Treatment Groups	First Injection
------------------	-----------------

Steroid Group	Triamcinolone 40 mg/1 mL (Kenalog) injection with 5 mL of 1% lidocaine
PRP Group	Platelet-rich plasma

*Blinding:*

Syringes will be prepared and masked with opaque tape by the clinic nurses, thus providing blinding for subjects.

A specimen of serum (from ~5mL of whole blood) and urine will be collected from the subject. If the subject's knee is aspirated prior to the injection (as commonly practiced), the synovial fluid will be collected, as well. These specimens will be deidentified and analyzed in the laboratory.

If the subject is randomized to the PRP group, the remainder of the PRP mixture not injected into the knee will be deidentified and analyzed in the laboratory.

Follow-Up/Clinic Visits:

Subjects will be required to complete VAS, KOOS-JR, and UCLA activity score surveys at baseline, 2 weeks, 4 weeks, 8 weeks, 12 weeks, 6 months, and 1 year. At the 4-week follow-up visit, urine and blood specimens will be collected as they were at the baseline visit. Synovial fluid collection will occur at this time point by a knee aspiration procedure.

Clinic follow-up evaluations will include a general assessment of appearance, range of motion, and function. ~~If the subject schedules another clinic visit within the one-year study timeline, subjects will be unblinded to which treatment arm they had received. At this visit or any time after, if an injection is indicated by participant pain and functionality scores, the participant has the choice to receive steroid or PRP injection, based on preference. If subjects in the PRP study arm experience severe pain, it is recommended to follow up with their physician for assessment and possible rescue therapy with corticosteroid injection. At any point during the study, the subject has the right to request rescue surgery and may proceed to do so with physician approval.~~

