**Deleted:**

The visits and all research activities are outlined below:

Baseline Visit:

- Consent/Randomization
- Objective Measures:
  - o Serum collection
  - o Urine collection
  - o Synovial fluid collection
  - o General assessments
- Subjective Measures:

- o VAS Pain
- o KOOS-JR
- o UCLA Activity
- Intervention:
  - o Initial injection based on treatment arm

2 Weeks (+/- 6 days) Surveys:

- Subjective Measures:
  - o VAS Pain
  - o KOOS-JR
  - o UCLA Activity

4 Weeks (+/- 1 week) Follow-Up:

- Objective Measures:
  - o Serum collection
  - o Urine collection
  - o Synovial fluid collection
  - o General assessments
- Subjective Measures:
  - o VAS Pain
  - o KOOS-JR
  - o UCLA Activity

8 Weeks (+/- 13 days) Surveys:

- Subjective Measures:
  - o VAS Pain
  - o KOOS-JR
  - o UCLA Activity

12 Weeks (+/- 2 weeks) Surveys:

- Subjective Measures:
  - o VAS Pain
  - o KOOS-JR
  - o UCLA Activity

6 Months (+/- 2 month) Surveys:

- Subjective Measures:
  - o VAS Pain
  - o KOOS-JR
  - o UCLA Activity

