**12 Months (+/- 2 month) Surveys:**

- Subjective Measures:
  - o VAS Pain
  - o KOOS-JR
  - o UCLA Activity

	Initial Visit	2 Weeks Surveys	4 Weeks Clinic Visit	8 Weeks Surveys	12 Weeks Surveys	6 Months Surveys	12 Months Surveys
Consent	X						
Randomization	X						
Serum Collection	X		X				
Urine Collection	X		X				
Synovial Fluid Collection	X		X				
General Assessments	X		X				
VAS Score (pain scale)	X	X	X	X	X	X	X
KOOS-JR	X	X	X	X	X	X	X
UCLA Activity	X	X	X	X	X	X	X
Injection	X						

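### A secondary objective compares single- with double-PRP injections, but double is undefined, neither arm is double-PRP and no second PRP injection is scheduled

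*Protocol*

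**What the plan says.** The Protocol, under Secondary objectives, includes this aim: "To assess differences in patient serum, urine, and synovial fluid biomarker concentrations between single- and double-PRP injections". It is one of 8 in the list. Nothing there or later says whether double means a second injection into the same knee after an interval, PRP in both knees, or something else.

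The rest of the Protocol describes the design as follows:

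- **Arms (Section VII, Enrollment/Randomization/Treatment Visit):** "Enrolled patients will be randomized to one of two treatment arms". The treatment table that follows has two rows, Steroid Group and PRP Group, and a single column for the first injection.
- **Size (Section VI):** "Approximately 70 participants will be enrolled. 35 to each arm if funding allows".
- **PRP administration (Section II):** "The PRP will be administered during the initial visit". The visit list in Section VII has one intervention entry, at baseline: "Initial injection based on treatment arm".
- **Specimens (Section VII, Follow-Up/Clinic Visits):** "At the 4-week follow-up visit, urine and blood specimens will be collected as they were at the baseline visit". Synovial fluid is also collected at that visit. The schedule table marks serum, urine and synovial fluid at the initial visit and week 4 only.
- **Bilateral patients (Section VII):** if a patient has a history of bilateral injections and "meets study requirements, randomization will occur for both knees".
- **Later injections (Section XI, Costs):** at a visit prompted by recurrent pain the participant is unblinded and may choose which injection to have, if one is indicated. The parallel text under Follow-Up/Clinic Visits is struck through.

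**The concern.** An objective should correspond to a comparison that the design forms and samples. Here one term, used once, carries the whole comparison, and the arms, injection schedule and specimen schedule do not say what it refers to.

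What is at stake is the reporting of one secondary result. After the data are in, several different contrasts could be presented under this objective: participants who chose a repeat against those who did not, PRP in both knees against PRP in one, or PRP in both knees against PRP in one and steroid in the other. They answer different questions. Any of them could be read as evidence on the number of PRP injections, although none isolates it.

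**Working it through.** The Protocol gives no figure for this objective to reproduce. The check is a count, followed by a test of each meaning that double could have.

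**Counts**

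| Item | Source | Result |
|---|---|---|
| Secondary objectives | Secondary objectives | 8, of which 1 is single versus double PRP |
| Planned allocation | Sections VI and VII | 2 arms × 35 = 70 |
| Left for a separate double-PRP group | Sections VI and VII | 70 − 70 = 0 |
| Time points | Schedule table: initial; 2, 4, 8, 12 weeks; 6, 12 months | 7 |
| Time points with an injection | Schedule table | 1 of 7 |
| Time points with fluids | Schedule table | 2 of 7 (initial, week 4) |
| Time points after week 4 with fluids | 8 and 12 weeks, 6 and 12 months | 0 of 4 |

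**Reading 1: a serial repeat.** No second PRP injection is scheduled. The only remaining route is the elective injection described in Section XI. Who receives it depends on recurrent pain and the participant's own choice after unblinding, so the comparison with non-repeaters is not randomised. The week-4 window is ± 1 week, so the last scheduled specimen falls no later than 4 + 1 = 5 weeks after the initial injection. The Protocol does not exclude an elective repeat before that, but it does not plan one. Ordinarily the repeat would come after the last specimen, which then cannot show its effect.

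**Reading 2: PRP in both knees.** Section VII randomises both knees of eligible bilateral patients, so some may receive PRP in both at the initial visit. Specimens are scheduled for them at baseline and week 4, although baseline synovial fluid depends on the knee being aspirated before the injection. Three limits apply:

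1. *Number.* The Protocol does not say how many participants will be bilateral, so neither the size of this group nor a detectable difference can be computed.
2. *Comparator.* Against participants with PRP in one knee only, the number of knees injected differs, but so does bilateral disease. The two cannot be separated. The Protocol does not say whether the two knees are randomised separately. If they are, there is a randomised contrast among bilateral participants, but it is PRP + PRP against PRP + steroid, so the steroid in the other knee differs too.
3. *Fluid.* Serum and urine are systemic and reflect both knees. Synovial fluid comes from one knee, and under this reading that knee has had one PRP injection in either group. The three fluids named in the objective would therefore not measure the same contrast.

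**Result.** Under reading 1 there is no planned group and no scheduled specimen. Under reading 2 specimens are scheduled, but the group is of unknown size and the comparison does not isolate single versus double PRP.

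**The case against.** The strongest reply is that the design can produce participants with two PRP injections. Randomising both knees is stated prospectively, and those participants have baseline and week-4 specimens. On that reading the objective has both patients and data, and defining the subset and handling two knees per person are matters that a statistical analysis plan commonly covers. This stands, and it limits the point: it would be wrong to say that no participant could contribute to the objective. It does not remove the point, because the Protocol never says that double means both knees. Nor could an analysis plan supply a scheduled second injection or a later specimen if a serial repeat is meant.

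A second reply is that the objective says only that differences will be assessed and claims no causal effect. That is fair. The fault lies in the missing definition and the mismatch with the design, not in an overclaim already made.

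A third is that the visible deletions in Section VII, and the treatment table's lone first-injection column, suggest that the objective is left over from a different design. A reader might infer this, but the document does not show it, and the objective itself is not struck through.

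**Conclusion.** The point holds as an inconsistency between a stated objective and the design. Double-PRP is undefined, 0 of 2 arms is double-PRP, and no second PRP injection is scheduled. As a serial comparison the objective cannot be answered from the scheduled specimens. As a both-knees comparison it can be described, but only in a subset of unstated size and confounded with bilateral disease.

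The consequence is ambiguous reporting of 1 of 8 secondary objectives. A reader might infer that the trial's main comparison or its power is weakened. The documents do not support that: the primary objective, the arms and the planned 35 per arm do not depend on this objective, and the Protocol gives no inputs from which a loss of power could be calculated.

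The conclusion assumes that the schedule table and visit list are complete for injections and specimens, and that the struck-through follow-up text is no longer in force. If that text were in force, it would add only the same unblinded choice of injection that Section XI describes.

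**What to change.** Reconcile the objective with Section II, the randomisation, blinding, follow-up and schedule parts of Section VII, and Section XI. Two options need only wording:

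- **Delete** the objective; or
- **Restate** it as a descriptive, exploratory comparison of participants with PRP in both knees and participants with PRP in one knee. Define double in those words, and name the baseline and week-4 specimens as the data used.

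A repeat-injection reading should not be kept, because no scheduled specimen could support it. Whether any participant should have a further injection is a clinical matter on which this point takes no position.

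The cost is that one secondary question is dropped or downgraded to exploratory. Visits, specimens, arms and sample size stay as they are.

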## II. Drugs/Biologics/Devices

The biologic under investigation in this study is platelet-rich plasma (PRP), a concentrated solution of platelets of autologous origin. This product will be produced from approximately 15 milliliters of whole blood by a venous blood draw performed by a clinical medical staff within the patient exam room. This sample will be placed into a centrifuge located in the clinical office to collate the platelets within the sample for proper collection of PRP. The 15 milliliters of whole blood will produce approximately 4-6 milliliters of PRP. The volume of PRP administered will be approximately 4-6 milliliters via intraarticular injection in the affected knee of patients with moderate-to-severe knee OA. This amount of PRP is indicated because standard knee injections (a large joint injection) range from 5-10 milliliters of medical substance. The PRP will be administered during the initial visit.

The current standard of care for treatment of moderate-to-severe knee OA involves serial, intra-articular injection of a corticosteroid, with injections performed, at minimum, three months apart. This modality has been shown to provide short-term relief of knee OA symptoms, possibly by modulating the immune response and associated inflammatory cascade and will be used as the reference therapy in this study. However, a limitation of this treatment is a lack of understanding of its impact upon OA pathophysiology, and specifically cartilage degeneration. PRP has been

selected for this study because it has been shown to provide pain relief and increase functionality when administered as described. Moreover, its beneficial effect may persist longer than that of corticosteroid injection, as well as remove the potential for cartilage degradation associated with intraarticular corticosteroid treatment. A corticosteroid study arm is also implemented to compare standard of care treatment to the PRP treatment population.

The medication used in the corticosteroid study arm is Triamcinolone Acetonide 40 mg/1 ml. The corticosteroid is to be ordered and regulated through the Investigational Pharmacy. The corticosteroid vials are to be stored in a lock box within the medical supplies room in the principal investigator's clinic. The medical supply room is up to IDS standards. Monthly temperature logs and expiration logs of the medication will be sent to IDS. The injection will consist of Triamcinolone 40 mg/1 mL (Kenalog) combined with 5 mL of 1% lidocaine and will be administered. The injection at the initial visit is the only established Triamcinolone injection within the study protocol. The participant may elect to receive an additional corticosteroid injection after 3 months after the initial injection if it is indicated by pain scores and physician clinical evaluation. This process may be repeated at other 3-month intervals within the study period, which is standard of care and an FDA approved use of the medication to control pain and treat the knee osteoarthritis.

An Investigational New Drug Application (IND) is not necessary for the products utilized in this study. We do not intend to report the investigation to the FDA as a well-controlled study in support of a new indication and with no intent to use it to support any other significant change in the labeling of PRP or triamcinolone. The use of these products does not involve a route of administration, dose, patient population, or other factors that significantly increases the risk associated with the use of the products. This investigation is not intended to promote or commercialize any of the products utilized.

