## **XI. Costs:**

Most costs to run this study, including the cost of the injections, the equipment to draw blood and collect urine, the containers to store the blood until the tests are run, and the assays run in the laboratory, will be covered by the department. Participants will not incur any of these costs.

The subjects will be financially responsible for all their standard of care treatment. The initial visit is a standard of care, and the participant will be responsible for covering the cost of the visit itself, not the injection procedure or other testing that may occur during the visit. The 4-week visit is not standard of care and will be covered through an internal research fund. Any clinical visit scheduled due to a reoccurrence of knee pain is standard of care and the participant may choose to receive another injection if indicated. The participant is unblinded during this visit and may choose their preference of injection type if indicated. The participant will accrue the cost of the visit and for the injection if the participant chooses to receive the procedure.

All assays and tests will be completed in the laboratory of the same hospital where samples are acquired, so there will be no transportation outside of the hospital.

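### Re-injection with unblinding is allowed during the year, but VAS, KOOS-JR and UCLA need not be recorded beforehand, so late patient-reported scores can reflect a later injection.

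*Protocol*

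**What the plan says.** Section II (Drugs/Biologics/Devices) schedules one triamcinolone injection, at the initial visit. A participant may elect another after three months "if it is indicated by pain scores and physician clinical evaluation", and "This process may be repeated at other 3-month intervals within the study period". The same section describes standard-of-care steroid injections as at least three months apart.

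Section XI (Costs) covers the participant who comes back in pain, on condition that there is an indication: "Any clinical visit scheduled due to a reoccurrence of knee pain is standard of care and the participant may choose to receive another injection". It goes on: "The participant is unblinded during this visit and may choose their preference of injection type if indicated". It states no interval of its own.

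Section VII (Follow-Up/Clinic Visits) fixes the measurements: "Subjects will be required to complete VAS, KOOS-JR, and UCLA activity score surveys at baseline", then at 2, 4, 8 and 12 weeks, 6 months and 1 year. Neither the visit list nor the schedule table has an unscheduled or pre-injection assessment.

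Two secondary objectives use these scores. One is "To evaluate the impact of PRP injection upon patient-reported outcome measures". The other relates baseline biomarkers to "treatment efficacy, based on patient-reported outcome measures, following PRP or corticosteroid injection".

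**The concern.** Retreatment is prompted by returning pain. The score that would show the first injection wearing off is the one taken just before the next injection, and the schedule does not ask for it. As an illustration, a participant who relapses at about month 3.5, is re-injected and feels well at month 6 could leave good scores at week 12 and month 6 and no required record of the relapse.

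The late scores bear on the rationale, since section II expects the benefit of PRP to outlast that of steroid. Some retreatment is foreseeable, because section III recruits people who have had repeated knee injections with benefit. The participant is also the assessor of these outcomes and the only party whom section VII describes as blinded. A score taken before unblinding is therefore the last blinded one that can be had. If it is not taken, an SAP can model it but cannot recover it.

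**Working it through.** The protocol gives no figure to reproduce. The check sets the permitted injection times against the survey windows.

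**Inputs.** Survey times and windows come from the visit list in section VII; the three-month rule for steroid comes from section II. Assumed conversions: three months = day 91; 6 months = day 182; 12 months = day 365; two months = 2 × 30.5 = 61 days.

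**Windows in days**

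| Survey | Calculation | Window |
|---|---|---|
| Week 2 | 14 ± 6 | 8–20 |
| Week 4 | 28 ± 7 | 21–35 |
| Week 8 | 56 ± 13 | 43–69 |
| Week 12 | 84 ± 14 | 70–98 |
| Month 6 | 182 ± 61 | 121–243 |
| Month 12 | 365 ± 61 | 304–426 |

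**Which scores can follow a repeat steroid (day 91 or later)**
- Weeks 2, 4 and 8 cannot: their windows close by day 69.
- Week 12 can on days 91–98: 8 of 29 days = 28%. With three months as day 90 it is 9/29 = 31%; as day 92, 7/29 = 24%.
- Months 6 and 12 can throughout their windows.

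**Is a survey window open on the day of a repeat steroid?** Days 91–365 are 275 days.
- Window open: 8 (week 12) + 123 (month 6) + 62 (month 12, days 304–365) = 193; 193/275 = 70%. Even then, nothing says whether the survey comes before or after the injection.
- No window open: days 99–120 (22) + days 244–303 (60) = 82; 82/275 = 30%. Taking two months as 62 or 60 days gives 29% or 31%.
- This share depends on stopping at day 365. Carried to the end of the month-12 window, days 91–426 are 336 days and the share is 82/336 = 24%.

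**Age of the last required score, surveys at nominal times**
- Week 12 to month 6: 182 − 84 = up to 98 days.
- Month 6 to month 12: 365 − 182 = up to 183 days.

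All of these are shares of days or gaps in days, not shares of participants. They describe repeat steroid under the three-month rule. They do not describe an injection given under section XI at another time. Before day 91, that could only be PRP, or a first steroid in a participant randomised to PRP.

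**Does any other current sentence require the scores?**
- Section II asks for pain scores before a repeat steroid, without naming the instrument, the order relative to unblinding, or recording as study data. It does not mention function.
- Section VII places the three instruments before the injection, as standard care, but under the enrolment and treatment visit.
- Section XII (General Physical Examination Findings) has staff review charts and patient-reported data at each clinical follow-up visit. That is review of existing data, not a new collection.

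**The case against.** The strongest reply is that the scores will probably be taken anyway. The schedule table labels the VAS as the pain scale, so the pain scores in section II are plausibly VAS. Section VII calls the three instruments standard care before the first injection, section XI calls the recurrence visit standard of care, and section XII has patient-reported data reviewed at follow-up visits. This stands in part. A reader might infer that re-injection needs no score at all, and the protocol does not support that: some pain score must be consulted before a repeat steroid. But no sentence requires all three instruments as study data before unblinding and re-injection.

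Second, a reader might infer that section XI allows steroid at any interval. It does not support that for repeat steroid: section II gives three months as the minimum, and section XI requires an indication.

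Third, a reader might see a contradiction between section XI and the text in section VII saying that "the participant has the choice to receive steroid or PRP injection, based on preference". That text is struck through and superseded, so the difference is not an error and nothing here rests on it.

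Fourth, retreatment is ethical, and its handling in the analysis belongs to the SAP. A treatment-policy or treatment-failure approach needs the injection date, which for in-clinic injections should largely be recoverable from the chart. All of that is granted. Other approaches need the score from before the injection, and whether it exists is settled by the protocol. Injections given elsewhere are not asked about in the surveys.

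Fifth, at nominal timing the week-12 survey (day 84) falls before the earliest repeat steroid and serves as a near pre-injection score. That is right for a repeat close to day 91. It helps less the later the injection comes.

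**Conclusion.** The point holds as a gap in data collection. The protocol allows re-injection with unblinding and choice of product, yet does not require VAS, KOOS-JR and UCLA to be recorded first. The 6- and 12-month scores, and 12-week scores from about day 91, can follow a later injection with no required score from just before it.

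The reach is limited to the secondary patient-reported objectives, mainly at late time points. A reader might infer that the primary biomarker objective is compromised. Under the three-month rule it is not affected by repeat steroid, because the 4-week sampling window closes on day 35. A reader might also take the 30% as the share of participants affected. It is a share of calendar days, and it falls to 24% over the longer period. With no retreatment rate in the protocol, the size and direction of any effect on the scores are unknown.

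The day counts rest on the conversions listed above. This is a worthwhile, inexpensive improvement, not a flaw that undermines the trial.

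**What to change.** In section VII and the schedule table:

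1. At any visit where a further knee injection is considered, collect VAS, KOOS-JR and UCLA before unblinding and before the injection. Count this as the scheduled survey if it falls inside a window, and continue all later surveys.
2. Record in the eCRF the date, product and knee of every later injection, and the date of unblinding. Add one survey question on knee injections given elsewhere. The knee is needed because section VII allows both knees to be randomised.

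The cost is protocol wording, a short form at a visit already taking place, one more survey question and a few eCRF fields, with no extra visits or participants. The change does not stop late scores from following a later injection. It supplies a score from just before it and shows who was retreated, when and with what. How those scores are analysed is left to the SAP.
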